7.2 Statistical Methods

Descriptive Statistics

Sample Size Computation and Power Analysis:

The sample size for this pilot study is set at 22 subjects for logistical and financial reasons. This is similar in size to other exploratory studies and will provide adequate data for estimation purposes for planning future studies. With 22 subjects, the study is intended to be for estimation purposes only.

Statistical Analysis Plan:

Data Analysis - The statistical analysis will provide descriptive summary statistics for categorical and continuous outcomes. Categorical variables will be described by their count and proportion of occurrence while continuous, normally distributed variables will be described by their mean and standard deviation; and continuous, non-normally distributed variables will be described by their median and range. The paired or unpaired Wilcoxon tests will be used to quantify differences in numerical outcomes while the McNemar's or Bowker's tests will be used to quantify changes in categorical variables. Complete response rate and complete/partial response rate and their corresponding 95% confidence intervals will be calculated and estimated using exact binomial method. Spaghetti plots will be used to visualize trend of the LPPAI score, PGA score, and Dermatology-QLI score at each time points for each individual. Effect sizes will be estimated for the appropriate statistical tests that will be used for group comparisons in future studies. This will enable more accurate power and sample size estimates moving forward.

Bioinformatic Analysis:

Bulk, Spatial, and Single-cell RNA Seq analysis: will be performed according to standard operating procedures of Mayo Clinic and University of Michigan genomics lab and bioinformatics. We will perform bulk, single cell and spatial sequencing pre and post therapeutically on tissue. Using these genomic techniques, we can determine differences within samples as well as between diseases in as few as 1-3 samples. Larger sample sizes will allow for confirmation of findings.

We will use bulk RNA sequencing to identify the enriched pathways of LPP and the pathway changes associated with treatment response. We will also define the single cell composition of LPP. We will examine the changes

pre and post therapeutic in each cell population in the tissue. We will identify the pathogenic T-cell as well as fibroblast based upon pre- and post- therapeutic changes of sub-populations of each cell type that correlate with response. Finally, we will map the pathogenic cells in space by integrating the single cell and spatial RNA sequencing data. This will allow us to determine a possible mechanism of action of both the T-cell inflammation and Fibroblast stimulation in LPP. Finally, we will validate our single cell and spatial findings using bulk RNA sequencing and immunohistochemical staining.

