Objectives	To evaluate the safety and efficacy of Deucravacitinib (BMS-986165) in Lichen Planopilaris and Frontal Fibrosing Alopecia as assessed by the change in Physician Global Assessment (PGA) of skin, oral mucosa, and hair, LPPAI. To predict responses through the identification of unique biomarkers of LPP at week 0 and utilizing bulk, spatial, and single-cell RNA sequencing					
Number of Subjects	22 (12 in cohort A and 10 in cohort B)					
Diagnosis and Main Inclusion Criteria	Adult patients with active LPP 1) 18 years old or older at time of consent 2) Biopsy proven diagnosis of LPP					
Study Product, Dose, Route, Regimen	Deucravacitinib (BMS-986165) 6 mg orally administrated, twice daily (Cohort A) and 6 mg orally QD (Cohort B).					
Duration of Administration	Drug will be administered from Day 0 through Week 24.					
Reference therapy	None					
Statistical Methodology	The statistical analysis will provide descriptive summary statistics for categorical and continuous outcomes. Categorical variables will be described by their count and proportion of occurrence while continuous, normally distributed variables will be described by their mean and standard deviation; and continuous, non-normally distributed variables will be described by their median and range.					

1 Introduction

This document is a protocol for a human research study. This study will be carried out in accordance with the applicable United States government regulations and Mayo Clinic research policies and procedures.

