
The risks of drawing blood include pain, bruising, lightheadedness, and/or fainting, or rarely, infection at the site of the needle stick.

Other:

As with all research, there is a chance that confidentiality could be compromised; however, we take precautions to minimize this risk.

2 Study Objectives

Primary Objective:

To determine the efficacy of Deucravacitinib (BMS-986165) as measured by Lichen Planopilaris Activity Index (LPPAI) score for overall response (Complete and partial responders) at week 24. Percent reduction of baseline LPPAI score after 24 weeks of treatment is defined as follows:

- Complete response: LPPAI reduction greater than 85% from baseline score.
- Partial response: LPPAI reduction between 25-85% from baseline score.
- Non-response: LPPAI reduction of less than 25% from baseline score.

The Lichen Planopilaris Activity Index (LPPAI) is a standardized validated quantitative measure of disease activity [12]. LPPAI score (0-10) is calculated as follows: (pruritus + pain + burning)/3 + (scalp erythema + perifollicular erythema + perifollicular scale)/3 + 2.5 (pull test) + 1.5 (spreading/2). Symptoms and signs are graded on a 4-point scale with 0 = absent, 1 = mild, 2 = moderate, and 3 =severe. Clinical progression and a positive hair pull test are graded 1 =yes; 0 =no.

Secondary Objective:

To determine the efficacy of Deucravactinib (BMS 986165)) as measured by the changes in PGA of scalp, DQLI score, VAS, VRS, NRS, and Skindex-16.(weeks 0 to 4, weeks 4 to 8, weeks 0 to 8, weeks 8 to 12, weeks 0 to 12, weeks 12 to 16, weeks 0 to 16, weeks 16 to 20, weeks 20 to 24, and weeks 0 to 24).

Exploratory Objectives:

To predict responses and examine the pharmacodynamics of treatment through the identification of unique biomarkers and transcriptomic changes of LPP at week 0 and utilizing single-cell RNA sequencing on responsive and non-responsive tissue at week 4 to correlate these biomarkers with measures of global response:

3 Study Design

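### A study meant for estimation plans no confidence interval for the change in any numerical outcome, only Wilcoxon tests, descriptive summaries and an unnamed effect size

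*Combined protocol and SAP*

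**What the plan says.** Section 7.2 (Statistical Methods) gives the purpose: "With 22 subjects, the study is intended to be for estimation purposes only". It gives the basis of the size as well: "The sample size for this pilot study is set at 22 subjects for logistical and financial reasons". The Study Summary splits the 22 patients into 12 in cohort A and 10 in cohort B.

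For analysis, section 7.2 provides:

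- **Numerical outcomes, summaries:** mean and SD if normally distributed; otherwise "continuous, non-normally distributed variables will be described by their median and range".
- **Numerical outcomes, comparisons:** "The paired or unpaired Wilcoxon tests will be used to quantify differences in numerical outcomes".
- **Categorical outcomes, changes:** "McNemar's or Bowker's tests will be used to quantify changes in categorical variables".
- **Response rates:** "Complete response rate and complete/partial response rate and their corresponding 95% confidence intervals will be calculated and estimated using exact binomial method".
- **Effect sizes:** to be estimated for planning later studies. No measure, time point, cohort or interval is given.

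The section states no significance level, no multiplicity rule and no designated interval for testing.

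Three places define which changes are of interest, and they differ. The secondary objective in section 2 names six scales (PGA, DLQI, VAS, VRS, NRS, Skindex-16) over ten intervals, starting "weeks 0 to 4, weeks 4 to 8, weeks 0 to 8". The outcome-measures text in section 3.1 lists 13 distinct intervals for NRS and at least 13 for Skindex-16. Section 3.5 sets the secondary endpoints at week 24 only, with five measures (VAS is not among them).

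**The concern.** If estimation is the purpose, the main product for each outcome should be an estimate with its uncertainty. The plan does this for the response rates and stops there. For the numerical scales, a reader gets a p-value and a summary.

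The summaries do not reliably fill the gap. A confidence interval cannot be recovered from a median and range. A mean and SD would suffice if they were those of the within-patient change, but section 7.2 does not say so. If they are given visit by visit, the SD of change also depends on the within-patient correlation. An effect size without a named measure or interval, from 10 to 22 patients, is a weak basis for sizing the next study, which is the use the plan has in mind for it.

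With many intervals listed, no test interval designated and no descriptive label, nominally significant intervals could also be picked out after the fact and read as findings.

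**Working it through.** **1. The plan's own figure.** No significance level, power, SD or precision target is stated, so 22 cannot be derived from a formula. The only check is 12 + 10 = 22, which agrees.

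**2. Precision of the missing intervals.** The 95% half-width for a mean change, in units of the SD of that change, is t(0.975, n−1)/√n:

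| n | Half-width |
|---|---|
| 12 (cohort A) | 0.635 SD |
| 10 (cohort B) | 0.715 SD |
| 22 (pooled) | 0.443 SD |

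The documents give no SD, so these cannot be put in scale points. They assume that every patient has a week-24 value. Withdrawn patients are not replaced (section 4.4.1), so losses would widen the intervals.

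For comparison, the exact binomial intervals already planned, at an assumed 50% response, are 21%-79% (6/12), 19%-81% (5/10) and 28%-72% (11/22).

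**3. Why visit-wise SDs are not enough.** With equal SD at both visits and correlation ρ, the SD of change is SD × √(2(1−ρ)). At ρ = 0.5 this is SD × √1.0 = 1.00 SD; at ρ = 0.8 it is SD × √0.4 = 0.63 SD. Both values of ρ are illustrative. The interval for change therefore cannot be rebuilt without ρ or the SD of change itself.

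**4. Multiplicity.** The 5% two-sided level is an assumption, since the plan sets none. With k tests and no true change, the expected number of false positives is at most 0.05k, and the chance of at least one under independence is 1 − 0.95^k.

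| Tests | k | Expected | P(at least one), independent |
|---|---|---|---|
| Five week-24 endpoints (section 3.5) | 5 | 0.25 | 0.23 |
| One scale, ten intervals (section 2) | 10 | 0.5 | 0.40 |
| Six scales × ten intervals (section 2) | 60 | 3.0 | 0.95 |

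Overlapping intervals on related scales are not independent. A simulation with no true change applied exact signed-rank tests to the ten intervals of section 2 (4,000 replicates; n = 10, 12 and 22). Correlation between visits was either constant at 0.5 or autoregressive at 0.8. The results were:

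- **One scale:** chance of at least one false positive about 0.29-0.33.
- **Six scales, correlated 0.5 or 0.8:** chance about 0.65-0.85, with 2.5-3.0 expected.

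**The case against.** The other side has a good deal right.

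- **The plan does contain estimates.** A reader might infer that it yields p-values in place of estimates. That goes too far. Means and SDs or medians and ranges are planned, effect sizes are promised, and the primary responder endpoint has exact 95% intervals. What is missing is the interval for a numerical change and the name of the effect-size measure.
- **The unpaired test is not an error.** A reader might take it as applied to within-patient change. The sentence concerns differences in numerical outcomes generally, and the design has independent groups (cohorts A and B) for which an unpaired test is correct. All that is lacking is a statement of which test serves which comparison.
- **Sixty tests are not planned.** A reader might multiply six scales by ten intervals and announce a 95% chance of a false positive. Section 7.2 does not say every listed interval will be tested, and section 3.5 confines the secondary endpoints to week 24. The 95% also needs independence and a 5% threshold that the plan never sets. Moreover, PGA and VRS are ordinal grades that may go to the categorical tests; without them the count is 4 × 10 = 40, with 2.0 expected and 1 − 0.95^40 = 0.87 even under independence.
- **Nominal p-values are ordinary in an open-label pilot** with no hypothesis or decision rule. Confining them to one interval is partly a matter of taste, and a descriptive label would serve as well.

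None of this supplies the missing intervals. Nor does section 3.5 fully settle the scope, because section 7.2 does not say whether it or the longer lists in sections 2 and 3.1 govern the testing.

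**Conclusion.** The point holds in limited form. For an estimation-only study, section 7.2 leaves every numerical change without an interval estimate and leaves the effect-size measure unnamed. The primary responder analysis is unaffected.

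The intervals would be wide: ±0.64 SD and ±0.72 SD for cohorts A and B, and ±0.44 SD pooled, assuming complete week-24 data and a t-based interval. That width is a reason to show them, since a point effect size alone would hide it.

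Multiplicity is secondary and depends on what is tested. At an assumed 5% level, the five week-24 endpoints give 0.25 expected false positives and about a 23% chance of any under independence, less if they are positively correlated. If all 60 listed changes were tested, up to 3 would be expected, with about a 65-85% chance of at least one under the correlations assumed. The 95% figure applies only under independence.

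**What to change.** In section 7.2:

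1. For LPPAI, DLQI, VAS, NRS and Skindex-16, report the paired week 0-24 change as a Hodges-Lehmann (or mean) estimate with a 95% confidence interval, by cohort.
2. Name the effect-size measure.
3. Label all p-values descriptive and unadjusted for multiplicity.
4. State that the signed-rank test is for within-patient change and the unpaired Wilcoxon test only for between-group comparisons.

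This is a wording change. It needs no new patients, visits or data. The cost is slightly more reporting, and intervals that will look wide at these sample sizes.

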7.3 Subject Population(s) for Analysis

• All-completed population: All subjects that receive at least one dose will be considered for analysis.

8 Safety and Adverse Events

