3.4 Primary Study Endpoints

Responders (complete and partial responses) by LPPAI score at week 24.

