4.4 Early Withdrawal of Subjects

4.4.1 When and How to Withdraw Subjects

- Subject safety issues
- Failure of subject to adhere to protocol requirements
- Disease progression
- Subject decision to withdraw from the study (withdrawal of consent)

Subjects who withdraw from the study for any reason will have their information recorded at the time of withdrawal. At the time of withdrawal, the subject will be considered at the final treatment date and will move into the treatment observation phase (4 weeks). Subjects will not be replaced. Follow up for subjects will continue to follow the normal follow up (Table-2)

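### The only analysis set is labelled All-completed but defined as all dosed, and no rule says how a dosed subject without a week-24 LPPAI enters the response rate

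*Combined protocol and SAP*

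**What the plan says.** Section 7.3 contains a single population: "All-completed population: All subjects that receive at least one dose will be considered for analysis". It does not call this set primary, but no other set is defined.

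The primary endpoint in Section 3.4 is "Responders (complete and partial responses) by LPPAI score at week 24". Section 2 defines the response categories only by percent reduction from baseline; the lowest is "Non-response: LPPAI reduction of less than 25% from baseline score". Section 7.2 gives the estimator, "Complete response rate and complete/partial response rate and their corresponding 95% confidence intervals will be calculated and estimated using exact binomial method", without naming a denominator or a rule for missing scores. The one instruction on missing data, in Section 9.3, concerns completing the case report form.

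Section 4.4.1 gives the reasons for withdrawal: safety, non-adherence, "Disease progression" and the subject's own decision. Subjects are not replaced. On what follows, it says "At the time of withdrawal, the subject will be considered at the final treatment date", after which the subject enters a 4-week observation phase. Section 4.4.2 repeats the 4 weeks. Section 4.4.1 also refers to normal follow-up under Table-2. Table 2 is the list of washout periods for biologic drugs; the visit schedule is Table-3.

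**The concern.** Completers and all dosed subjects are different sets as soon as one treated subject leaves early, and here one sentence names the first and defines the second. The wording that dosed subjects are to be considered for analysis does not settle whether each of them counts in the denominator.

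This matters because some of the missing scores are likely to depend on outcome. A subject withdrawn for progression is a treatment failure. If that subject has no week-24 score and the analyst works with completers, the failure disappears from the primary result. The study has no control arm in which a similar loss could offset it. Section 7.2 says "With 22 subjects, the study is intended to be for estimation purposes only", and the estimates are meant to size future studies, so the response rate is itself the product.

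**Working it through.** **The plan's own figures.** The sample size was set on logistical and financial grounds, so there is no power, precision or dropout calculation to reproduce. The one sum that can be checked agrees: 12 (cohort A) + 10 (cohort B) = 22.

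**Who has no week-24 score.** A subject who withdraws at week w is observed until week w + 4. This falls short of week 24 when w + 4 < 24, that is, when w < 20. Such a subject ends follow-up without a week-24 LPPAI unless the reference to normal follow-up means staying on the full visit schedule. That reference points to the wrong table, and Section 3.3 sets the follow-up epoch at 4 weeks. A subject who withdraws from about week 20 onward can still be scored at or after week 24, off drug.

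**How that subject is classified.** Complete, partial and non-response all need a percent reduction at week 24. With no score, none of the three applies, and Section 7.2 does not fill the gap.

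**Effect of the denominator.** Inputs: N = 22 from the Study Summary and Section 7.2, and the exact (Clopper-Pearson) 95% interval from Section 7.2. The number of observed responders x and the number d without a week-24 score are assumptions, because the documents give neither.

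- All dosed, missing counted as non-response: x/N
- Missing dropped: x/(N − d)
- Inflation factor: N/(N − d)

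With x = 11, the all-dosed rate is 11/22 = 50.0% (28.2 to 71.8) whatever d is.

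| d | Missing dropped | 95% CI | Rise (points) | Factor |
|---|---|---|---|---|
| 2 (9%) | 11/20 = 55.0% | 31.5 to 76.9 | 5.0 | 1.10 |
| 4 (18%) | 11/18 = 61.1% | 35.7 to 82.7 | 11.1 | 1.22 |
| 6 (27%) | 11/16 = 68.8% | 41.3 to 89.0 | 18.8 | 1.375 |

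For x between 8 and 14, the rise is 3.6 to 6.4 points (d = 2), 8.1 to 14.1 (d = 4) and 13.6 to 23.9 (d = 6).

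By cohort, with 2 missing and half responding:

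- A: 6/12 = 50.0% (21.1 to 78.9) becomes 6/10 = 60.0% (26.2 to 87.8).
- B: 5/10 = 50.0% (18.7 to 81.3) becomes 5/8 = 62.5% (24.5 to 91.5).

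**When dropping overstates the rate.** Suppose r of the d missing subjects would have been responders. The full-data rate is (x + r)/N, and dropping overstates it when r/d < x/(N − d). With x = 11 and d = 4, the condition is r < 4 × 11/18 = 2.4. At r = 2 the full-data rate is 13/22 = 59.1%, below 61.1%; at r = 3 it is 14/22 = 63.6%, above it. The upward bias therefore needs leavers to respond less often than stayers. That is to be expected for progression withdrawals but is not assured for the other reasons.

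**Using the score at withdrawal.** A subject who leaves for progression would ordinarily show a reduction below 25% and so counts as a non-responder, exactly as under the missing-as-non-response rule. The two rules differ for subjects who leave for other reasons while improved by at least 25%. If all d were of that kind, the rate would be (11 + d)/22: 13/22 = 59.1%, 15/22 = 68.2% or 17/22 = 77.3% for d = 2, 4 or 6. These are upper limits.

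**The case against.** The strongest reply is that the definition is the operative text and already names the inclusive set, so the label is only a misnomer. No section restricts the analysis to completers or says that withdrawn subjects are dropped. This stands: a reader might infer a planned completer analysis from the label, but the documents do not support that. It does not close the point, because including a subject in the set does not say how that subject is scored when the week-24 LPPAI is missing.

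A reader might also infer that taking the score at withdrawal favours the drug for progression withdrawals. It does not, for the reason shown in the working. That reading is in any case strained, since a final treatment date most naturally marks the end of dosing and not a substitute endpoint visit.

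Nor does every withdrawal lose the week-24 score. Those from about week 20 onward may have one, and the absence of a score before then is inferred from the 4-week phase, not stated in the plan.

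Finally, this is an estimation-only pilot with no null rate, success threshold or go/no-go rule. The shifts tabulated for the total of 22 lie within the wide exact interval around the all-dosed rate, and the individual plots in Section 7.2 would show early stops. All of this lowers the severity. It does not supply the missing rule, and a shift in the point estimate carries into the planning of the next study.

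**Conclusion.** The concern holds as an unresolved denominator. The label and the definition of the only analysis set conflict, and a dosed subject without a week-24 LPPAI has no place in the response rate as written. A completer denominator is therefore open to the analyst and would remove subjects who failed early.

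Under the assumed 11 responders, and 2 to 6 of 22 subjects without a score, the choice moves the rate by 5.0 to 18.8 points. Both counts are assumptions. Reading the difference as upward bias further assumes that those who leave respond less often than those who stay.

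This should be fixed before the data are analysed. The documents do not support a graver charge, because they plan no exclusion and attach no decision threshold to the rate.

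**What to change.** - **Section 7.3:** rename the set All-treated and state that the denominator is all dosed subjects, overall and by cohort. The cohort denominators are 12 and 10 only if every planned subject is dosed. Those are enrolment targets, and Section 3.1 allows for 14 pre-treatment samples in cohort A, so take the counts from dosing records.
- **Sections 3.4 and 7.2:** state that a responder needs a week-24 LPPAI meeting the criterion, and that a dosed subject without one counts as a non-responder. Say whether an off-drug score at week 24 from a late withdrawal is used.
- **Section 7.2:** report the observed-case rate as a sensitivity analysis only, with the number missing and the reasons.
- **Sections 4.4.1 and 4.4.2:** reconcile the final-treatment-date wording, the 4-week phase and the normal follow-up, including the reference to Table-2, which is not the visit schedule.

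The cost is a few sentences and no added subjects. The reported rate may be slightly lower. Counting every missing score as non-response is a conventional choice and one of several defensible ones; what matters is that it is fixed in advance.
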